9.1.2. Summary Measure

AUC(0-∞) and Cmax following single dose, and AUC(0- τ) and Cmax following repeat dose will be summarized descriptively (mean, standard deviation, median, minimum, maximum, geometric mean, and the standard deviation, CV% and 95% confidence interval (CI) of log-transformed parameters) by dose cohort.

Tmax will be summarized descriptively using non-transformed values.

In addition, the following assessments will be performed:

9.1.3. Population of Interest

All pharmacokinetic analyses will be based on the PK population, unless otherwise specified. All summaries, figures and data listings will use treatment labels specified in Section 5.1.

9.1.4. Statistical Analyses / Methods

Details of the planned displays are provided in [Appendix 10: List of Data Displays](#) and will be based on GSK Data Standards and statistical principles.

Unless otherwise specified, endpoints / variables defined in Section 9.1.1 will be summarised using descriptive statistics, graphically presented (where appropriate) and listed.

GSK2816126 plasma concentration-time data will be listed for each subject and summarized by planned time point and dose cohort. It is noted that the urine and bile concentration data will not be analysed due to unavailability of data.

Pharmacokinetic parameters will be listed and summarized descriptively (mean, standard deviation, median, minimum, maximum, geometric mean (excluding tmax and %AUCex), and the standard deviation, CV% and 95% confidence interval (CI) of log-transformed parameters) by dose cohort.

The following pharmacokinetic statistical analyses will only be performed, if sufficient data is available (i.e. if subjects have well defined plasma profiles).

9.1.4.1. Dose proportionality

If data permits, dose proportionality will be assessed using power model for:

- AUC(0-∞) and Cmax on Cycle 1 Day 1 (C1D1)
- AUC(0- τ) and Cmax on Cycle 1 Day 1 and Cycle 1 Day 15 (C1D15)

Dose proportionality of GSK2816126 AUC(0-∞) and Cmax following single dose administration and AUC(0-τ) and Cmax following repeat dose administration will be evaluated using the power model as described below:

$$\log(\text{pharmacokinetic parameter}) = a + b * \log(\text{dose})$$

where a is the intercept and b is the slope.

The power model will be fitted by restricted maximum likelihood (REML) using SAS Proc Mixed. Both the intercept and slope will be fitted as fixed effects. If there is sufficient data, the model may also be fit with the intercept and/or slope as random effects depending on the ability of the model to converge and on estimation of variance-covariance matrix. The mean slope and corresponding 90% confidence interval will be estimated from the power model.

10. PHARMACODYNAMIC ANALYSES

The statistical analysis for Tri-methylated Histone H3 lysine 27 (H3K27me3) biomarker will be detailed and reported in a separate document and may not be included in the main clinical study report.

12. APPENDICES

12.1. Appendix 1: Protocol Deviation Management and Definitions for Per Protocol Population

12.1.1. Exclusions from Per Protocol Population

There will be no Per Protocol population used for any displays or statistical analysis.

12.2. Appendix 2: Schedule of Activities

12.2.1. Protocol Defined Schedule of Events

Refer to Protocol Amendment 4 Section 7.1.

12.3. Appendix 3: Assessment Windows

No assessment windows will be applied.

12.4. Appendix 4: Study Phases and Treatment Emergent Adverse Events

12.4.1. Study Phases

Assessments and events will be classified according to the time of occurrence relative to treatment start date.

Study Phase	Definition
Pre-Treatment	Date ≤ Study Treatment Start Date
On-Treatment	Study Treatment Start Date < Date ≤ Study Treatment Stop Date + 30 days
Post-Treatment	Date > Study Treatment Stop Date + 30 days

Some datasets include the first dosing day as On-Treatment and some exclude the first dosing date as On-Treatment. The first dosing day (Day 1) is considered Pre-Treatment for ECOG, ECG, vital signs, liver events, lab tests, cardiac scan, and other safety domains. The first dosing day (Day 1) is considered to be On-Treatment for adverse events and concomitant medications.

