1. INTRODUCTION

The purpose of this reporting and analysis plan (RAP) is to describe the analyses to be included in the Clinical Study Report for Protocol

GlaxoSmithKline Document Number	Date	Version
2012N149024_00	11-JUL-2013	Original
2012N149024_01	23-OCT-2013	Amendment No. 1

Applies only to sites in the UK. Following review of the protocol by the MHRA, the following changes were made:

1. Removed wording from the protocol stating that GSK2816126 treatment will continue until commercial availability.
2. The stopping criterion based on QTc will be changed to ≥ 500 msec.
3. Added a QTc stopping criterion that patients will be withdrawn if they experience an increase in QTc > 60 msec from baseline following dose reduction and re-challenge.

2012N149024_02 30-OCT-2013 Amendment No.: 02

Applies to all study sites. Following review of the protocol by the Food and Drug Administration (FDA), the following changes were made:

1. The starting dose of GSK2816126 is reduced from 125 mg/dose to 50 mg/dose
2. Updated Dose Limiting Tox language
3. Revised 100% dose escalation wording
4. Decreased QTc baseline exclusion criterion
5. Added regular ECG monitoring timings
6. Added blood glucose testing to our list of clinical lab tests
7. Removed any wording pertaining to the use of central labs
8. Removed wording from the protocol stating that GSK2816126 treatment will continue until commercial availability
9. Clarify that PET scans are optional
10. Elaborated on CT scan timings

11. The stopping criterion based on QTc will be changed to \geq 500 msec
12. Added a QTc stopping criterion that subjects will be withdrawn if they experience an increase in QTc $>$ 60 msec from baseline following dose reduction and re-challenge
13. Added explanatory language to T&E Table around coagulation, CT and standalone PET assessments
14. Changed corticosteroid exclusion criteria

2012N149024_03	03-APR-2015	Amendment No. 03
----------------	-------------	------------------

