5.2. Baseline Definitions

For laboratory data, baseline values are defined as the most recent, non-missing value from a local laboratory prior to the first dose of study treatment.

For ECG analyses, subject level baseline is defined as the mean of triplicate Cycle 1 Day 1 (C1D1) pre-dose QTc results.

Parameter	Study Assessments Considered as Baseline			Baseline Used in Data Display
	Screening	Day -1	Day 1 (Pre-Dose)	
Efficacy				
Disease Assessment	X			Screening
Safety				
Vital Signs	X		X	Day 1 Pre-dose if collected, otherwise, use screening
ECG	X		X	Mean of triplicate pre-dose measurements on Day 1, if not available, use mean values at screening
Clinical Chemistry, Hematology	X		X	Day 1 Pre-dose if collected, otherwise, use screening

Parameter	Study Assessments Considered as Baseline			Baseline Used in Data Display
	Screening	Day -1	Day 1 (Pre-Dose)	
Coagulation	X			Screening
PK/PD				
PK Concentration			X	Day 1 Pre-dose
PD Biomarker			X	Day 1 Pre-dose

Unless otherwise stated, if baseline data is missing no derivation will be performed and the baseline data will be set to missing.

The baseline definition will be footnoted on all change from baseline displays.

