7.4. Other Safety Analyses

The analyses of non-laboratory safety test results including ECGs and vital signs will be based on GSK Core Data Standards, unless otherwise specified. The details of the planned displays are presented in [Appendix 10: List of Data Displays](#).

Vital Signs

Listing of vital signs including Systolic BP, diastolic BP, heart rate, body temperature, height and weight at each scheduled visit will be provided.

ECOG (Eastern Cooperative Oncology Group) Performance Status

A summary of worst case post-baseline ECOG status shift from baseline among all visits by dose level will be provided. A supporting listing including performance status and change from baseline will also be provided.

ECG

A summary of the number and percentage of subjects who had normal and abnormal ECG findings will be displayed by scheduled visits as well as for the worst case post-baseline for each dose level. A listing of abnormal ECG findings will be provided. ECG interval values will also be listed.

The mean of ECG values at each collection point will be used for ECG analyses

Summary of the worst case QTc (QTcF and QTcB) post-baseline values relative to baseline will be provided by dose level. The QTc values (QTcF and QTcB) will be

rounded to the integer and the values will be categorized into the following ranges: Grade 0 (<450), Grade 1 (450-480), Grade 2 (481-500), and Grade 3 (≥ 501).

Summary of the worst case QTc (QTcF and QTcB) increase from baseline by dose level will be provided. The categories of 'Increase of ≤ 30 msec' 'Increase of 31-60 msec' and 'Increase of > 60 msec' will be used. A summary of change in QTc value will display the number and percentage of subjects with a change within each category in the worst case post-baseline among all visits.

Baseline results are defined by the nearest timepoint prior to first dose. The baseline QTc value is determined by the mean of the triplicate Cycle 1 Day 1 (C1D1) pre-dose QTc results. If these results are not available, then the mean of QTc of the screening triplicate QTc results would be used. Subjects with a missing baseline value will be assumed to have a normal baseline value.

LVEF (Left Ventricular Ejection Fraction)

LVEF results will be listed with subject level details including absolute change from baseline. Only the post-baseline assessments that used the same method (ECHO or MUGA) as the baseline assessments will be used to derive the change from baseline.

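### The Day 1 phase rule goes by calendar date, so an ECG or laboratory reading taken after the first infusion starts is neither baseline nor On-Treatment and may drop out of the worst-case tables

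*SAP*

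**What the plan says.** Section 12.4.1 sets phase from dates alone. Pre-Treatment is "Date ≤ Study Treatment Start Date" and On-Treatment is "Study Treatment Start Date < Date ≤ Study Treatment Stop Date + 30 days". The text below the table then splits the first dosing day by data type:

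- Measured safety data: "The first dosing day (Day 1) is considered Pre-Treatment for ECOG, ECG, vital signs, liver events, lab tests, cardiac scan, and other safety domains".
- Events and medications: "The first dosing day (Day 1) is considered to be On-Treatment for adverse events and concomitant medications".

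Baseline is defined elsewhere, and by dose rather than by day. For ECG, Section 5.2 says "subject level baseline is defined as the mean of triplicate Cycle 1 Day 1 (C1D1) pre-dose QTc results", and its table gives "Mean of triplicate pre-dose measurements on Day 1, if not available, use mean values at screening"; Section 7.4 repeats this. For laboratory data, Section 5.2 takes the last non-missing value before the first dose.

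The displays at issue are in Sections 7.3, 7.4 and 12.10.7. For QTc, Section 7.4 states "Summary of the worst case QTc (QTcF and QTcB) increase from baseline by dose level will be provided" (Table 3.14), with a companion table of worst post-baseline category (Table 3.13). Table 3.12 shows ECG findings by visit and for the worst case after baseline. Tables 3.8, 3.9 and 3.11 give worst-case laboratory changes.

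**The concern.** Two rules that should meet at the first dose do not. Baseline ends at the start of the first infusion; On-Treatment begins the next calendar day. Readings in between have no analysis role unless post-baseline is understood independently of phase, and the SAP does not say that it is.

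QTc is where this matters most. Cardiac parameters are part of the Part 1 primary endpoint (Section 2.2). The amendment history in Section 1 records QTc stopping criteria of 500 msec or more, and of a rise above 60 msec from baseline after dose reduction and re-challenge, added following regulatory review. The drug is given intravenously, with 2-hour infusions mentioned in Section 2.3, so an ECG after the first infusion can fall on Day 1. Section 9.1.4.1 uses Cycle 1 Day 1 Cmax for dose proportionality, so the SAP treats Day 1 exposure as informative. During accelerated titration there was one subject per dose level (Section 2.3), so one omitted reading could change a whole column of the table.

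**Working it through.** The SAP gives no figure to reproduce, so the check applies its rules to one reading: an ECG or laboratory sample on Day 1 after the first infusion has started.

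1. **Phase (12.4.1).** The date of the reading equals the treatment start date. It satisfies date ≤ start date and fails start date < date. It is Pre-Treatment, and the sentence on Day 1 confirms this for ECG and laboratory tests.
2. **Baseline (5.2, 7.4).** The reading is after dose, so it cannot be baseline.
3. **Result.** It is neither baseline nor On-Treatment.
4. **Use in the worst-case tables.** This depends on what post-baseline means:

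| Reading of post-baseline | Day 1 post-infusion value |
|---|---|
| Taken from the On-Treatment phase | Excluded from the worst-case part of Table 3.12, from Tables 3.13 and 3.14, and from the worst-case laboratory tables if such samples exist |
| Anything after the pre-dose baseline | Included |

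The SAP does not choose. Two things point to the first row: the phase table is the only general rule for placing assessments relative to treatment, and the SAFE_L2 shell in Section 12.11 labels its derived row as worst case on therapy.

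5. **Direction.** Let A be a subject's readings from Day 2 onward and B the Day 1 post-infusion readings. Then max(A) ≤ max(A and B together). Leaving out B can only give an equal or milder worst case.
6. **Example with assumed values.** Suppose a subject's Day 1 post-infusion QTc rises more than 60 msec from baseline and all later rises are 30 msec or less. The first row of the table puts the subject in the lowest category of Table 3.14; the second puts the subject in the highest.
7. **Comparison with adverse events.** Sections 12.4.1 and 12.4.2 make Day 1 On-Treatment for adverse events. If the rise in step 6 were reported as an event, the event would be treatment-emergent while the ECG that showed it was Pre-Treatment.

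**What is not touched.** Vital signs have only a listing (Section 7.4, Listing 15) and no summary table. The by-visit rows of Table 3.12 do not depend on phase. Listings 11 to 13 still show the laboratory and ECG interval readings, and Listing 14 shows abnormal ECG findings.

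**The case against.** The strongest reply is that no exclusion is stated. The ECG tables say post-baseline, and a reading after a pre-dose baseline is post-baseline in the ordinary sense. Section 7.3 runs the gradable laboratory summary over all scheduled visits without a phase filter, and the on-therapy wording appears in one listing shell only. This stands in part: the loss is a likely reading, not an express instruction. It does not remove the defect, because two competent programmers could produce different QTc tables from the same text.

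Second, the schedule is in the protocol, which is not shown. The line "Added regular ECG monitoring timings" in the amendment summary names no day or hour. Post-dose Day 1 ECGs are plausible; nothing in the SAP points to post-dose Day 1 laboratory samples. If all Day 1 samples were pre-dose, the rule does no harm to them. This stands, and it limits the confidence.

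Third, the consequence is bounded. Part 1 is descriptive (Section 2.4), the report is abbreviated (Section 2.1), dose decisions used in-stream data and the totality of evidence (Section 3.1), and Day 1 adverse events are tabulated.

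Three stronger readings are tempting and not supported:

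- **That all Day 1 safety data are lost.** Adverse events are On-Treatment, vital signs have no summary to drop out of, and the measured values remain listed.
- **That a subject who stops after one dose has no post-baseline ECG.** On-Treatment runs to 30 days after the stop date, so any ECG from Day 2 to the end of that window counts.
- **That the loss can be sized.** With k independent occasions, one of them on Day 1, and chance p per occasion of crossing a category, the share crossing is 1 − (1 − p)^k with Day 1 and 1 − (1 − p)^(k−1) without. For k = 2, p = 10% this is 19% against 10%; for k = 2, p = 5%, 9.8% against 5.0%; for k = 4, p = 10%, 34% against 27%. Both k and p are invented, and repeated QTc readings in one subject are correlated, so these figures say nothing about this trial.

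**Conclusion.** The concern holds for ECG and QTc, and for any post-dose Day 1 laboratory samples. Section 12.4.1 states a rule that puts post-dose readings in the Pre-Treatment phase, against the pre-dose baseline in Sections 5.2 and 7.4 and against the SAP's own treatment of Day 1 adverse events. Loss from the worst-case tables follows if post-baseline is taken from the On-Treatment phase, which is the likelier reading but not a stated one.

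The direction is certain under that reading: equal or milder. The size is unknown and is zero if no ECG or laboratory reading was taken after dose on Day 1. This is a correction that should be made before the final analysis, with moderate confidence. It does not show that the safety record is incomplete.

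**What to change.** In Section 12.4.1:

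- Classify Day 1 ECG and laboratory records by date and time relative to the start of the first infusion: before it, Pre-Treatment; after it, On-Treatment.
- If clock time is missing, use the planned time-point label. If both are missing, keep the current Pre-Treatment class and flag the record in the listing.
- State that worst-case post-baseline includes all readings after the start of the first infusion. The separate rule in Section 12.5.2 that keeps unscheduled visits out of summary tables is not changed by this.

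Leave the baseline definitions in Sections 5.2 and 7.4 as they are.

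The cost is one extra flag derivation and a sentence or two of SAP text, with no new data. The downside is reliance on recorded times or time-point labels, which may be incomplete for some Day 1 records.

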12.4.1.1. Study Phases for Concomitant Medication

Study Phase	Definition
Prior	If medication end date is not missing and is before 28 days prior to screening visit
Concomitant	Any medication that is not a prior

NOTES:

- Refer to [Appendix 7](#): Reporting Standards for Missing Data for handling of missing and partial dates for concomitant medication. Use the rules in this table if concomitant medication date is completely missing.

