6.6. Concomitant Medications

Concomitant medications will be coded using GSK Drug coding dictionary, and summarized. The summary of concomitant medications will show the number and percentage of subjects taking concomitant medications by Ingredient. Multi-ingredient products will be summarized by their separate ingredients rather than as a combination of ingredients. Anatomical Therapeutic Chemical (ATC) classification Level 1 (Body System) information will be included in the dataset created but will not appear on the listing or summary.

In the summary of concomitant medications, each subject is counted once within each unique ingredient. For example, if a subject takes Amoxycillin on two separate occasions, the subject is counted only once under the ingredient “Amoxycillin”. In the summary of concomitant medications, the ingredients will be summarized by the base only, using CMBASECD and CMBASE.

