12.10.4. Study Population Tables

Study Population Tables					
No.	Population	IDSL / Example Shell	Title	Programming Notes	Deliverable [Priority]
Subject Disposition					
1.1.	All Subjects	ES1	Summary of Subject Disposition	ICH E3, FDAAA, EudraCT	SAC [1]
1.2.	Enrolled	NS1	Summary of Number of Participants by Country and Site ID	EudraCT/Clinical Operations	SAC [1]
Protocol Deviation					
1.3.	All Subjects	DV1	Summary of Important Protocol Deviations	ICH E3	SAC [1]
Demographic and Baseline Characteristics					
1.4.	All Subjects	DM1	Summary of Demographic Characteristics	ICH E3, FDAAA, EudraCT	SAC [1]
1.5.	Enrolled	DM11	Summary of Age Ranges	EudraCT Age categories: 18-64, 65-74, 75-84 and ≥85	SAC [1]
1.6.	All Subjects	DM5	Summary of Race and Racial Combinations	ICH E3, FDA, FDAAA, EudraCT	SAC [1]
Prior and Concomitant Medications					
1.7.	All Subjects	MH1	Summary of Current/Past Medical Conditions	ICH E3	SAC [1]
1.8.	All Subjects	CM1	Summary of Concomitant Medications	ICH E3	SAC [1]
1.9.	All Subjects	LA1	Summary of Disease Burden at Screening		SAC [1]
1.10.	All Subjects	DC2	Summary of Disease Characteristics at Screening for Subjects with Solid Tumors Including Prostate Cancer		SAC [1]
1.11.	All Subjects	DC2	Summary of Disease Characteristics at Screening for Subjects with Lymphomas		SAC [1]
Exposure and Treatment Compliance					
1.12.	All Subjects	OEX5	Summary of Exposure to Study Treatment	ICH E3 Calculate dose intensity per cycle.	SAC [1]

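### The rule for concomitant medication is tied to screening and has no end point, so Table 1.8 can count drugs that never overlapped with study treatment (minor)

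*SAP*

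**What the plan says.** SAP Section 12.4.1.1 has two classes for medications. Prior applies "If medication end date is not missing and is before 28 days prior to screening visit". Concomitant is "Any medication that is not a prior". A note adds: "Use the rules in this table if concomitant medication date is completely missing". A record with no end date is therefore Concomitant.

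Section 12.4.1, directly above, sets phases relative to study treatment. On-Treatment is "Study Treatment Start Date < Date ≤ Study Treatment Stop Date + 30 days" and Post-Treatment is "Date > Study Treatment Stop Date + 30 days". It then adjusts the first day for some data types: "The first dosing day (Day 1) is considered to be On-Treatment for adverse events and concomitant medications".

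Section 6.6 describes the output: "The summary of concomitant medications will show the number and percentage of subjects taking concomitant medications by Ingredient". Each subject counts once per ingredient. In Section 12.10.4 this is Table 1.8, "Summary of Concomitant Medications", on the All Subjects population. Its programming note does not restrict the period. Section 6.1 has it shown by dose cohort and overall.

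**The concern.** A table of concomitant medications is normally read as showing what subjects took alongside the study drug. Under Section 12.4.1.1 a drug can enter that table although its use ended before the first dose. The rule also sets no point after treatment at which a newly started drug stops counting. The medication table would then cover a different period from the adverse event tables, because the treatment-emergent flag in Section 12.4.2 runs from treatment start to treatment stop plus 30 days.

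A reader could not correct for this from the planned output. Section 6.6 mentions a listing of concomitant medications, but Appendix 10 (Listings 1 to 31) contains none. Table 1.8 is the only planned display of these drugs and it carries no dates.

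At stake is whether a background table gives the right counts by ingredient. No tested hypothesis depends on it.

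**Working it through.** The SAP states no figure to reproduce, so the check applies the rule as written to example records and compares the result with the phases of Section 12.4.1.

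**Inputs**
- Prior if the end date is present and end date < screening − 28 days; otherwise Concomitant (Section 12.4.1.1).
- Treatment window: treatment start, with Day 1 counted as On-Treatment for medications, to treatment stop + 30 days (Section 12.4.1).
- Interval from screening to first dose: not given in the SAP. Assumed to be 1, 14 or 28 days.

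**Early end.** The longest gap between stopping a drug and first dose at which the drug is still Concomitant is 28 + (screening-to-dose interval):
- interval of 1 day: 28 + 1 = 29 days
- interval of 14 days: 28 + 14 = 42 days
- interval of 28 days: 28 + 28 = 56 days

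**Example records**

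| Record | Class by 12.4.1.1, interval 1 / 14 / 28 days | Position against the 12.4.1 window |
|---|---|---|
| Ended 43 days before first dose | Prior / Prior / Concomitant | before it |
| Ended 35 days before first dose | Prior / Concomitant / Concomitant | before it |
| Ended 20 days before first dose | Concomitant in all three | before it |
| Ended 1 day before first dose | Concomitant in all three | before it |
| Ongoing over treatment | Concomitant in all three | inside it |
| Started 31 days after last dose | Concomitant in all three | after it |
| Started 120 days after last dose | Concomitant in all three | after it |
| Both dates missing | Concomitant in all three | cannot be excluded |

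**Direction.** A drug classed as Prior ended before screening, and so before first dose. The rule therefore never drops a drug that overlapped with treatment; it can only count too many. Section 12.7.2.1 pushes the same way, because partial stop dates are imputed to the end of the month and to December, which moves records out of Prior.

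**Limit.** Because Section 6.6 counts a subject once per ingredient, the count rises only for subjects whose entire recorded use of an ingredient lay outside the window. The SAP gives nothing from which to estimate how many there are.

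**The case against.** The strongest reply is that Section 12.4.1.1 is a specific rule for medications and governs over the general phases of Section 12.4.1. *Concomitant* is then a defined term, and a deliberately wide net misses no co-medication. Much of this stands. The two sections use different labels, so a reader who infers that the SAP gives one variable two conflicting values goes too far. What remains is a poor fit: the remark about Day 1 implies a treatment-based phase for medications, yet neither the definition in Section 12.4.1.1 nor Table 1.8 uses one. The wide net may be intended, but the SAP does not say so and does not split the table by period.

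Three stronger readings are tempting and not supported:
- **That Table 1.8 serves to explain adverse events, QTc changes or PK.** The SAP does not say this, and no planned analysis in Sections 7 or 9 takes the Prior/Concomitant class as an input.
- **That drugs started long after the last dose will in fact appear.** The rule would admit them, but whether they are recorded depends on how long the eCRF collects medications, which is not shown.
- **That percentages by cohort will be badly distorted.** One wrongly counted subject is 100 points at a dose level with one subject. In the overall column, with the 30 to 40 subjects planned in Section 2.3, it is 1/40 to 1/30, or 2.5 to 3.3 points. These figures show how coarse the percentages are, not how many records are misclassified.

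**Conclusion.** The point holds as a minor one. As written, the rule counts drugs stopped before first dose as concomitant, with a reach back of 29 to 56 days if the screening-to-dose interval is 1 to 28 days. That interval is an assumption. For drugs stopped between screening and first dose the conclusion does not depend on it. At the late end the defect is the missing upper limit; its practical effect is unknown.

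Only Table 1.8 is affected. Part 1 is descriptive (Section 2.4), the report is an abbreviated CSR (Section 2.1), and no primary endpoint, DLT, response or PK result changes.

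**What to change.** Replace the table in Section 12.4.1.1 with three classes tied to the SAP's own treatment window:
- **Prior:** ended before treatment start.
- **Concomitant:** overlaps the period from treatment start (Day 1 included) to treatment stop + 30 days. Ongoing or missing end dates count as overlapping unless the start date falls after that window.
- **Post-treatment:** started after treatment stop + 30 days.

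Build Table 1.8 on the concomitant class so defined, and say so in its programming note. This also gives the Day 1 remark in Section 12.4.1 a function.

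The cost is a few lines of SAP wording and a derivation flag; no new data are needed. The small downside is that drugs stopped shortly before first dose leave Table 1.8; they can be kept in a separate prior category. If the wide definition is intended, the minimum is to state that in Section 12.4.1.1, footnote it on Table 1.8, and reconcile it with Section 12.4.1.
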